4.2.1 Primary Endpoint

4.2.1.1 PN Volumes and Derivation of REiNS Tumour Response

For all patients, the REiNS tumour data will be used to determine each patient's visit response according to the REiNS criteria. Tumour assessments will be measured by volumetric MRI.

Baseline radiological tumour assessments will be performed during the 28-day screening period. Unless clinically indicated otherwise, tumour assessments of the target and non-target PN (if relevant) will be obtained at screening and every 4 cycles (16 ± 1 weeks) relative to the date of the first dose for the first 24 cycles. From the end of Cycle 24, tumour assessments will be performed every 6 cycles (24 ± 1 week) as long as the patient remains on study intervention.

Volumetric MRI assessment will be performed by AstraZeneca's appointed imaging contract research organisation (CRO) according to the REiNS criteria. A double read of all MRI scans will be performed. The ICR reviewers will be blinded to the study intervention group. Further details of the ICR will be documented in the independent review charter (IRC).

All volumetric MRI scans for all patients (including those at unscheduled visits or outside visit windows) will be collected on an ongoing basis and sent to an AstraZeneca-appointed imaging CRO for central analysis. The investigator will select the target PN and non-target PN (if relevant) based on the results of the screening PN assessments. Details about target PN location and non-target PN location (if relevant) will also be collected and sent to the imaging CRO to ensure that the independent reviewer also follows the most clinically relevant PN. The imaging CRO will determine the tumour measurements of the target PN and non-target PN.

If an unscheduled assessment is performed (e.g., to investigate clinical signs/symptoms of progression) and the patient has not progressed, the subsequent assessments at the next scheduled visit must be performed. This schedule is to be followed in order to minimise any unintentional bias caused by some patients being assessed at a different frequency than other patients.

To determine the level of response, the TL and NTL volume will be assessed as the average PN volumes from the double read, and follow-up scans will be compared to the baseline scan or the scan at the time of best response after documenting a CR/PR for the same PN.

If the interim analysis takes place, then:

- At DCO1, if only part of a PN was imaged on post-baseline scans, the ICR will outline that same part of the PN (partial PN volume) at all timepoints. The detailed handling of partial volumes in the ICR data can be found in the IRC.
- At the primary analysis (DCO2), two sets of parameters will be produced from the ICR due to different handling of the partial volumes. The first set of parameters will contain results that are not adjusted for partial volumes occurring after DCO1, that is, any partial volume for timepoints after DCO1 which captures a different PN part than the outlined PN part used at DCO1 will be assessed as NE. Any partial volume for timepoints after DCO1 which captures the same PN part as the outlined PN part used for the partial volume at DCO1 will be assessed. The second set of parameters will contain results that are adjusted for partial volumes after DCO1, that is, if there is a partial volume after DCO1 which captures a different PN part than the outlined PN part used at DCO1, then all timepoints will be adjusted to outline the same part of the PN at all timepoints.

In order to keep responses of the patients included in both the interim and the primary analyses consistent across review periods (i.e., responses reported at DCO1 will remain unchanged at DCO2 for patients having partial volumes after DCO1), a third set of parameters will be programmatically derived by proportionally scaling up partial volumes after DCO1. At each post-baseline visit after DCO1, partial volumes will be re-derived as follows: (post-baseline partial volume * baseline full volume) / baseline partial volume. Partial volumes can be selected from the second set of parameters, while baseline full volume will be provided in the first set of parameters.

All the analyses using PN volumes performed at DCO2 will use the just mentioned scaled partial volumes after DCO1 data (third set of parameters) and the non-adjusted partial volume after DCO1 (first set of parameters) will be supportive.

Otherwise, if the interim analysis does not take place, then at the primary analysis (DCO2), all the analyses using PN volumes performed at DCO2 will use the first set of parameters.

At the final DCO, two sets of parameters will be produced from the ICR due to different handling of the partial volumes. The first set of parameters will contain results that are not adjusted for partial volumes occurring after DCO2, that is, any partial volume for timepoints after DCO2 which capture a different PN part than the outlined PN part used at DCO2 will be assessed as NE. The second set of parameters will contain results that are adjusted for partial volumes after DCO2, that is, if there is a partial volume after DCO2 which captures a different PN part than the outlined PN part used at DCO2 then all timepoints will be adjusted to outline the same part of the PN at all timepoints.

At the final DCO, similar to the approach at DCO2, post-DCO2 partial volumes will be scaled up to make sure that responses previously reported will remain unchanged and post-DCO2 partial volumes are proportionally adjusted. Each post-DCO2 partial volume will be multiplied by baseline partial volume and then divided by baseline full volume.

The primary endpoint analysis performed at the final DCO will use the scaled partial volumes after DCO2 data (third set of parameters), and a supplementary analysis will be performed using the unadjusted partial volume after DCO2 (first set of parameters).

All the analyses using PN volumes performed at final DCO will use the (third set of parameters with scaled partial volumes after DCO2 data, while the non-adjusted partial volume after DCO2 (first set of parameters) will be supportive.

Using the REiNS criteria, a change in volume from baseline of 20% is used to indicate a clinically significant increase or decrease of PN volume from baseline. For all patients, the target PN (see Section 4.2.1.2) and non-target PN (see Section 4.2.1.3), if applicable, will be assessed, both will be given a response (see [Table 5](#) and [Table 6](#)), and any new PNs (see Section 4.2.1.4) will be recorded.

If the two independent readers disagree on the presence of a new lesion, an adjudication will be performed, and the adjudicator decision regarding the presence or absence of the new lesion will be used for the assessment. At each visit, patients will be programmatically assigned an overall REiNS visit response of CR, PR, stable disease (SD), or progressive disease (PD) using the information from target PNs, non-target PNs, and new PNs and depending on the status of their disease compared with baseline and previous assessments (see [Table 7](#)). If a patient has a PN assessment that cannot be evaluated, then the patient will be assigned a visit response of not evaluable (NE).

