4.2.1.9 Primary Analysis of the Primary Endpoint

The primary analysis will include all randomised patients (FAS). Data obtained using on-treatment MRI volumetric assessments (see Section 3.3.2.1), from first dose up until progression (if progression occurs prior to the end of Cycle 16), or the last evaluable assessment up to and including the end of Cycle 16 assessment in the absence of progression will be included in the assessment of the ORR and by excluding MRI during prolonged study intervention interruption (while-on-treatment strategy). For the complete intercurrent event strategy, refer to Section 4.2.1.7.

If the interim analysis takes place, the ORR by the end of Cycle 16 at DCO2 will be analysed using the ICR data with the scaled partial volume after DCO1 as described in Section 4.2.1.1 (third set of parameters).

The formal statistical analysis will be performed to test the following hypotheses for the primary analysis:

- H_0 : ORR selumetinib = ORR placebo.
- H_1 : ORR selumetinib \neq ORR placebo.

The ORR will be compared at the landmark end of Cycle 16 between selumetinib versus placebo using a Fisher's exact test with the significance level stated in Section 3.3.7. The ORR by the end of Cycle 16 in each treatment group will be presented with corresponding 2-sided exact 95% confidence interval (CI) based on the Clopper-Pearson method (Clopper and Pearson 1934). The risk difference and 95% CI based on the Miettinen-Nurminen (score) method (Miettinen and Nurminen 1985) will also be presented.

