5 INTERIM ANALYSIS

The interim analysis (DCO1) is expected to occur after the 100th randomised patient has had the opportunity to complete their end of Cycle 16 assessment. This corresponds to approximately 68.5% of the primary endpoint information expected at the primary analysis (DCO2). As it is expected that all 145 patients will have completed Cycle 12 by the time the 100th randomised patient has completed Cycle 16, the information fractions for the key secondary endpoints are estimated to be 100% at the interim analysis. See Section [3.3.7](#) for details on the multiplicity testing approach.

The interim analyses will be performed by a team of unblinded statisticians and programmers independent from AstraZeneca and reviewed by an Unblinded Review Committee. If the URC recommends the study team to be unblinded, the results of these analyses may form the basis of submissions for regulatory approval. If the interim analysis DCO (DCO1) is due to take place within approximately 4 months of the primary analysis DCO (DCO2), then the interim analysis may not be performed and only the primary analysis will be performed.

For further details of the interim analysis including which outputs will be provided to the URC, please refer to the URC Charter and the Interim Analysis SAP.

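### If the interim takes place, DCO2 scaling of partial volumes from baseline breaks the volume series at DCO1, so a stable tumour with an unconfirmed PR can fail confirmation or be called PD

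*SAP*

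**What the plan says.** SAP 4.2.1.1 sets out three versions of the volume data for DCO2, to be used if the interim takes place.

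- Set 1: a later scan showing a different part from the one used at DCO1 is not evaluable.
- Set 2: when a later scan shows a different part, "then all timepoints will be adjusted to outline the same part of the PN at all timepoints".
- Set 3: built so that "responses reported at DCO1 will remain unchanged at DCO2 for patients having partial volumes after DCO1". The rule is "At each post-baseline visit after DCO1, partial volumes will be re-derived as follows: (post-baseline partial volume * baseline full volume) / baseline partial volume", with the sources given as: "Partial volumes can be selected from the second set of parameters, while baseline full volume will be provided in the first set of parameters".

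Set 3 is the main data for all volume analyses at DCO2, and set 1 is supportive. For the primary endpoint, SAP 4.2.1.9 states that "the ORR by the end of Cycle 16 at DCO2 will be analysed using the ICR data with the scaled partial volume after DCO1". Set 2 feeds the formula but is not itself analysed.

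For response, "follow-up scans will be compared to the baseline scan or the scan at the time of best response after documenting a CR/PR". Under SAP 4.2.1.2 (Table 5), PR is a fall of at least 20% from baseline. PD is a rise of at least 20% from baseline, or from best response after a PR. Confirmation requires CR or PR at the next consecutive scan, with no missed or non-evaluable visit between. SAP 5 adds that "it is expected that all 145 patients will have completed Cycle 12 by the time the 100th randomised patient has completed Cycle 16".

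**The concern.** Set 3 joins two series measured on different bases. Up to DCO1 it holds the reported volume, normally the whole tumour. After DCO1 it holds the baseline volume multiplied by the relative change of one part. That assumes the unseen part has changed like the seen part ever since baseline, although the scans before DCO1 already show how the whole changed.

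Two decisions are made across the join: whether a first PR is confirmed, and whether volume has risen 20% from best response. A step created by the derivation can decide either. At stake are the confirmed response rate in the primary endpoint and, over later scans, single-arm ORR, BOR, DOR, PFS and TTP. SAP 4.2.1.3 sends partial non-target volumes through the same rule.

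**Working it through.** **Inputs.** The rule and the 20% limits are those cited above. Protocol 9.2 and SAP 3.4 give 146 randomised, 73 per arm, and assumed ORR of 20% against 0%. SAP 5 puts the interim at the 100th participant, with 68.5% of the information. The documents give no tumour volumes, so those below are illustrative: whole 100 mL at baseline, imaged part 60 mL, remainder 40 mL.

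**1. The plan's own figures.** 100/146 = 68.5%, which reproduces (100/145 would give 69.0%). Fisher's exact test with 73 per arm and 20% against 0% has power 99.8% at alpha 0.05 and at 0.047, in line with the stated figure above 99%.

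**2. The jump.** Let f be the change of the whole and p the change of the part, both from baseline to the last scan before DCO1. That scan is reported as full(baseline) x (1 + f). If nothing changes afterwards, the next scan is derived as full(baseline) x (1 + p). The step is (1 + p)/(1 + f) - 1, which is zero only if p = f.

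**3. Stable tumours after DCO1.**

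| Whole before DCO1 | Part | Derived after DCO1 | Result |
|---|---|---|---|
| 78 mL (-22%, PR) | 49.2 mL (-18%) | 49.2 x 100/60 = 82 mL (-18%) | PR not confirmed |
| 70 mL (-30%, PR) | 51 mL (-15%) | 51 x 100/60 = 85 mL; 85/70 = 1.214 | PD from best response |
| 84 mL (-16%, SD) | 47.4 mL (-21%) | 47.4 x 100/60 = 79 mL (-21%) | new PR |

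The unseen 40 mL must have changed by -28% in row 1 (40 to 28.8), -52.5% in row 2 (40 to 19) and -8.5% in row 3 (40 to 36.6). Row 1 needs modest heterogeneity; row 2 needs strong heterogeneity.

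**4. General conditions.** A first PR fails confirmation if f is -20% or lower and p is above -20%. It becomes PD if p is at least 1.2(1 + f) - 1, that is -4% at f = -20%, -10% at f = -25% and -16% at f = -30%.

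**5. Reach in the primary ORR.** Only 146 - 100 = 46 participants can have a Cycle 16 scan after DCO1, about 23 of them on selumetinib. If all have passed Cycle 12 by then, each has one scheduled scan after DCO1 that counts. Exposure therefore needs a first PR at Cycle 12, a Cycle 16 scan showing a different part, and p and f on opposite sides of a limit. Failed confirmation and PD have the same effect on ORR: a non-responder.

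**6. Bound on the test.** At 20%, 23 participants give about 4.6 responders. Losing all of them leaves 14.6 - 4.6 = 10 expected responders, or 10/73 = 13.7%. Fisher power against 0% at alpha 0.047 is then still about 95%.

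**7. Final DCO.** The last part of SAP 4.2.1.1 multiplies a post-DCO2 partial volume by baseline partial and divides by baseline full. A part unchanged at 60 mL becomes 60 x 60/100 = 36 mL, or -64% from 100 mL. That is the inverse of the DCO2 rule and scales down, although the text describes scaling up.

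**The case against.** The case against a large effect is strong, and most of it stands.

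- **Confirmed responses.** A reader might infer that a confirmed response can be lost. It cannot if both scans precede DCO1, because those results are kept. Only a first, unconfirmed response is at risk.
- **False responders.** A reader might infer that the primary ORR can be inflated. With everyone past Cycle 12 at DCO1, a stable tumour has one later scan by Cycle 16, which can yield only an unconfirmed PR. The protocol's information fractions of 95.2% and 94.8% (9.1) would leave about 4 to 8 participants (84 x 0.048 = 4.0; 146 x 0.052 = 7.6) with both scans after DCO1, so this limit rests on the SAP's expectation.
- **Frequency.** Protocol 8.1.1 asks sites to check that the tumour is fully visible. The documents give neither the number of partial scans nor the heterogeneity within tumours, so no rate of misclassification can be derived.
- **Conditional use.** The rule lapses if the interim is skipped, and ORR is tested again at DCO2 only if it failed at DCO1. DOR and single-arm PFS and TTP are descriptive.
- **Supportive analysis.** Set 1 blocks a false PR or PD from scaling. It does not restore a lost confirmation, because a non-evaluable visit also breaks it.
- **Trade-off.** A baseline-scaled change from baseline uses two readings of the part. A linked one uses four readings, although reading errors shared by part and whole at one scan partly cancel. For comparison with the last scan before DCO1, the count is reversed. Linking also still assumes that the unseen part follows the seen part after DCO1. This is a reason to keep the baseline-scaled version as a sensitivity analysis, but it does not remove the step.

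The independent review charter, which the SAP cites for detail on partial volumes, was not available.

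**Conclusion.** The concern holds in a limited form. If the interim takes place and a later scan shows a different part, the derived series steps by (1 + p)/(1 + f) - 1 at DCO1 even in a stable tumour. In the primary ORR, a first PR not yet confirmed at DCO1 can then fail confirmation or be classed as PD. At most about 23 selumetinib participants are exposed, and probably far fewer.

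False PR can arise in single-arm ORR and BOR, and false PD can shorten DOR, PFS and TTP. The primary test is unlikely to turn on this; the estimates could shift by an amount the documents do not allow one to calculate. The conclusion assumes that part and whole changed differently before DCO1, and that the SAP's expectation on Cycle 12 is met. The inverted final-DCO formula is an error regardless of either assumption. This should be corrected, but it does not threaten the trial's main conclusion.

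**What to change.** Link the series at t0, the participant's last evaluable scan before DCO1:

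volume(t) = reported volume(t0) from set 1 x part(t)/part(t0) from set 2.

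In row 1 of the table this gives 78 x 49.2/49.2 = 78 mL, still a PR. All DCO1 responses are kept, which is the SAP's stated aim. With no post-baseline scan before DCO1, t0 is baseline and the present formula returns.

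Use the same link for non-target volumes. At the final DCO, link at the last evaluable scan before DCO2 and delete the inverted formula. Keep the baseline-scaled version as a sensitivity analysis, and report how many participants have rescaled scans and whose category differs between the two.

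The cost is a change to two SAP formulas and their programs. No new reads are needed, because set 2 already outlines the same part at every timepoint. The change should be made before unblinded volumes are seen.

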4.2.1.3 Non-Target PN Response

Only one non-target PN may be selected. Non-target PN must also be clinically relevant and measurable by volumetric MRI. Partial non-target PN volumes will be handled following the strategy in Section [4.2.1.1](#). This section provides the definitions of the criteria used to determine and record a response for the non-target PN at each MRI assessment.

Non-target response will be derived using the PN volume over both ICR assessments as follows:

Table 6: Non-Target PN Visit Responses (REiNS)

Visit responses	Description
Progressive disease (PD)	Unequivocal progression of an existing non-target PN. In this study, unequivocal progression is defined as an increase in the volume of the non-target PN by 20% or more compared to baseline.
Non-progressive disease (non-PD)	Insufficient volume change to qualify for PD.
Not applicable (NA)	No non-target PN recorded at baseline.
Not evaluable (NE)	Data unavailable for non-target PN assessment.

PD, progressive disease; PN, plexiform neurofibroma; REiNS, Response Evaluation in Neurofibromatosis and Schwannomatosis.

Table 6 is based on the recommendations from [Dombi et al 2013](#).

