4.2.3.2 Best Objective Response Definition

The best objective response (BOR) will be calculated based on the overall visit responses from each on-treatment MRI assessment, as described in [Section 0](#). It is the best response a patient has had following the start of intervention, but prior to starting any subsequent NF1-PN therapy and up to and including progression or the last evaluable MRI assessment in the absence of progression. The categorisation of BOR will be based on REiNS using the following response categories: cCR, CR, cPR, PR, SD, PD, and NE.

The different ways of achieving a BOR of cCR, CR, cPR, or PR are shown in [Table 11](#).

Table 11: Scenarios for Best Objective Response

Post-baseline Visit N	Post-baseline Visit N+1	BOR
PR	PR/CR	Confirmed PR (cPR)
PR	SD/PD/NE	Unconfirmed PR
CR	CR	Confirmed CR (cCR)
CR	PR/SD/PD/NE	Unconfirmed CR
SD/NE	CR	Unconfirmed CR
SD/NE	PR	Unconfirmed PR
NE	NE	NE

BOR, best objective response; CR, complete response; NE, not evaluable; PD, progressive disease; PR, partial response; SD, stable disease.

BOR will be determined programmatically based on REiNS from the overall visit response using all data up until the first progression event or the last evaluable MRI assessment in the absence of progression. BOR will be derived using the on-treatment MRI volumetric assessments (see [Section 3.3.2.1](#)). The denominators will be consistent with those used in the single-arm ORR analysis.

Patients with no post-baseline MRI assessments will be considered as non-responders. For patients whose progression event is death, the BOR will be calculated based on all evaluable MRI assessments prior to death using the while on-treatment MRI volumetric assessments (see [Section 3.3.2.1](#)).

At DCO2, the BOR will be analysed using the ICR data with the scaled partial volume after DCO1 (third set of parameters) as described in Section 4.2.1.1 .

At the final DCO, the BOR will be analysed using the ICR data with the scaled partial volume after DCO2 (third set of parameters) as described in Section 4.2.1.1.

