4.2.3.4 Primary Analysis of Single-Arm ORR

The primary analysis will include all patients randomised to selumetinib (selumetinib FAS), that is, a single arm assessment of ORR. Data obtained from the first selumetinib dose up until progression or the last evaluable assessment in the absence of progression, and while on-treatment MRI volumetric assessments (see Section 3.3.2.1) will be included in the assessment of single-arm ORR. Data are included as outlined in Section 4.2.3.1, adhering to the intercurrent event strategy (refer to Section 4.2.3.3).

The ORR will be presented with a corresponding 2-sided exact 95% CI based on the Clopper-Pearson method (Clopper and Pearson 1934).

Analyses will occur at DCO1, DCO2, and the final DCO. At DCO2 and the final DCO the partial volume strategy defined in Section 4.2.1.1 will be used for this endpoint. At DCO2, the ORR will be analysed using the scaled partial volumes after DCO1 (third set of parameters). At the final DCO, the ORR will be analysed using the scaled partial volumes after DCO2 (third set of parameters).

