4.2.4 Duration of Response

4.2.4.1 Definition

For the subset of patients who have a cCR or cPR, DOR will be defined as the time from the date of the first documented response (which is subsequently confirmed) until the date of documented progression as assessed by ICR per REiNS criteria or death due to any cause. DOR will be derived using the while on-treatment MRI volumetric assessments (see Section 3.3.2.1). The end of response should coincide with the MRI assessment of progression or death from any cause used for the progression-free survival (PFS) endpoint (see Section 4.2.5). The date of the first documented response will be defined as the latest of the dates contributing towards the first response of PR or CR which is subsequently confirmed.

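### The final-DCO formula for rescaling partial PN volumes is the inverse of the DCO2 formula, so it shrinks volumes it is meant to scale up and can hide progression

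*SAP*

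**What the plan says.** SAP 4.2.1.1 sets out three sets of volume parameters for scans that show only part of a PN. The third set, derived by program, puts partial volumes back on the full-tumour scale. At DCO2, if the interim analysis took place, the derivation is "post-baseline partial volume * baseline full volume) / baseline partial volume" (the opening bracket falls just before the quoted words).

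For the final DCO the section says it follows the DCO2 approach and that "post-DCO2 partial volumes will be scaled up to make sure that responses previously reported will remain unchanged". The operation it then gives is "Each post-DCO2 partial volume will be multiplied by baseline partial volume and then divided by baseline full volume".

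The third set is the main data for all final-DCO analyses of PN volume; the non-adjusted first set is supportive. SAP 4.2.3.2 and 4.2.3.4 repeat this for the final DCO: "the BOR will be analysed using the ICR data with the scaled partial volume after DCO2" and "the ORR will be analysed using the scaled partial volumes after DCO2". SAP 4.2.1.2 sends partial target volumes to the same strategy, and 4.2.1.3 does so for the other lesion: "Partial non-target PN volumes will be handled following the strategy in Section" 4.2.1.1. As to the comparator, "follow-up scans will be compared to the baseline scan or the scan at the time of best response after documenting a CR/PR". The final-DCO paragraph does not say whether the baseline is then the full or the partial volume.

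**The concern.** The final-DCO instruction contradicts both its stated aim and the formula it claims to follow. Nothing elsewhere in the SAP corrects it. It matters for post-DCO2 scans that capture a different part of the PN from the part outlined at DCO2, where baseline partial volume is smaller than baseline full volume.

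The most direct risk is missed progression, because PD needs no confirming scan. An affected scan can fail to register PD in the target PN (from baseline or from best response) or in the non-target PN. That can lengthen PFS and TTP. It can lengthen DOR too, since "The end of response should coincide with the MRI assessment of progression" used for PFS.

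BOR can gain an unconfirmed PR. Single-arm ORR, TTR and entry to the DOR analysis change only if a false PR is confirmed by, or confirms, an adjacent PR. Long-term and fed-state percentage-change summaries (SAP 4.2.18.4) can be pulled towards shrinkage.

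**Working it through.** **Inputs**

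- F = baseline full volume; P = baseline partial volume; f = P/F. The documents do not give f, so 0.95, 0.90 and 0.80 are illustrative assumptions.
- r = post-baseline partial volume ÷ P, the true relative volume of the imaged part. The post-baseline partial volume is therefore r × P.
- Thresholds (SAP Table 5): PR at a decrease of 20% or more from baseline; PD at an increase of 20% or more from baseline or from best response.

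**Step 1: the DCO2 formula**

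V = (r × P) × F/P = r × F, so V/F = r. The true change is recovered for every f.

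**Step 2: the final-DCO formula as written**

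V = (r × P) × P/F.

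- Against the full baseline: V/F = r × f².
- Against the partial baseline: V/P = r × f.

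The scaling factors are 1/f and f. Their product is 1, so they are reciprocals and agree only at f = 1. The full baseline is the more natural comparator, because the DCO2 formula returns volumes to that scale. Neither comparator recovers r.

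**Step 3: what is read**

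Columns 2 to 4 use the full baseline. PD needs r ≥ 1.2/f² against the full baseline and r ≥ 1.2/f against the partial baseline.

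| f | Unchanged PN reads | True +20% reads | True growth needed for PD (full) | True growth needed for PD (partial) |
|---|---|---|---|---|
| 0.95 | −9.8% | +8.3% | +33% (1.2/0.9025 = 1.330) | +26% (1.2/0.95 = 1.263) |
| 0.90 | −19.0% | −2.8% | +48% (1.2/0.81 = 1.481) | +33% (1.2/0.90 = 1.333) |
| 0.80 | −36.0% | −23.2% | +88% (1.2/0.64 = 1.875) | +50% (1.2/0.80 = 1.500) |

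The full-baseline multiples also apply to regrowth from a best response that was measured on a full scan before DCO2.

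**Step 4: cut-offs for a visit-level false PR**

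- Full baseline: an unchanged PN reads as PR when f ≤ √0.8 = 0.894; a PN that truly grew 20% reads as PR when f ≤ √(0.8/1.2) = 0.816.
- Partial baseline: the cut-offs are 0.800 and 0.8/1.2 = 0.667.

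**Step 5: worked example**

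Baseline full 500 mL, baseline partial 450 mL (f = 0.9), later partial 585 mL. True change: 585/450 = 1.30, or +30%.

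- DCO2 formula: 585 × 500/450 = 650 mL; 650/500 = 1.30, PD.
- Final-DCO formula as written: 585 × 450/500 = 526.5 mL; 526.5/500 = 1.053, or +5.3%, stable disease.

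**Step 6: how many scans are exposed**

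DCO2 comes when the last participant dosed can have reached the end of Cycle 16; the final DCO comes at about 24 cycles. For a participant dosed k cycles before the last one, the post-DCO2 scans are the scheduled ones (Cycles 4, 8, 12, 16, 20, 24, 30, 36, 42, 48) falling in (16 + k, 24 + k]. For k from 0 to 24 that is always 1 or 2. False confirmed responses should therefore be few, but one scan is enough to miss progression.

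**The case against.** The inversion itself cannot be argued away; the case on the other side concerns weight and direction.

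- *The intent is plain.* The correct formula stands a few paragraphs earlier and the text says the volumes go up, so a programmer may well implement the right version. That is true, but the SAP is the prespecified instruction: following it gives wrong volumes, and departing from it silently is an undocumented deviation. If the interim analysis is skipped, DCO2 uses the first set, and the inverted formula is then the only rescaling applied.
- *Few scans may be affected.* Protocol 8.1.1 asks sites to check that the PN is fully visible before sending scans. This should limit partial volumes, and it stands as a reason for caution about size.
- *The bias need not run one way.* A falsely small volume could become the best-response reference and create false PD later. At f = 0.90, a stable responder at r = 0.75 would read 0.75 × 0.81 = 0.6075; a later full scan entered at 0.75 would be 0.75/0.6075 = 1.235, or +23.5%. This needs the later scan to enter unscaled. The second set outlines the same part at all timepoints, which points instead to rescaling every post-DCO2 visit of an affected participant. The text does not settle it, so in responders the direction is conditional.
- *The supportive analysis is a safeguard.* It is a weak one. In the first set these scans are not evaluable, so it supplies no alternative volume. The second set would expose the error, but it is not named as a supportive analysis.
- *No confirmatory result is at risk.* Correct, and it limits the severity.

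**Conclusion.** The final-DCO formula is wrong as written. It is the reciprocal of the DCO2 formula and contradicts the stated aim of scaling up. Against the full baseline the ratio read is r × f² in place of r; against the partial baseline it is r × f.

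Essentially unaffected are ORR by the end of Cycle 16, the randomised-period endpoints, the formal tests at DCO1 and DCO2, and visit responses already reported at DCO2. Exposed are the final-DCO single-arm, time-to-event and descriptive outputs. The sizes above rest on assumed values of f and mainly on the full baseline as comparator. With f and the number of affected participants unknown, the effect on the actual results cannot be estimated. It should be corrected, but it does not threaten the trial's main conclusions.

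**What to change.** Before final-DCO programming, replace the sentence in SAP 4.2.1.1 so that it matches the DCO2 formula: rescaled volume = post-DCO2 partial volume × baseline full volume ÷ baseline partial volume. Add that the result is compared with the baseline full volume, or with the volume at best response where that rule applies. A reminder that this covers target and non-target PN is optional, since SAP 4.2.1.2 and 4.2.1.3 already say so. The cost is one or two sentences in the SAP, with no new data and no added resource.
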